**1. Background/Rationale/Literature Review**

The disproportionate impact of stroke on minorities is well-established. Racial and ethnic disparities have been observed in all aspects of stroke including prevalence of risk factors, awareness and health-care related beliefs, access to stroke care and treatments, stroke incidence, severity, and mortality, and acute “clot-busting” treatment with tissue plasminogen activator (tPA) and preventive medications (Cruz-Flores 2011). For example, African-Americans (AA) are more likely to die and be disabled after stroke and half as likely to receive tPA compared to non-Hispanic whites (Johnston 2001, Hsia 2011). In acute stroke, though approximately 63% of stroke patients in the US arrive to the hospital by EMS, AA and Hispanics are less likely to utilize EMS than non-Hispanic whites (Ekundayo 2013). Race-ethnic disparities in arrival to hospital and EMS use are even more staggering in Chicago, where AA patients arrive later and Hispanics utilize EMS less than non-Hispanic whites. Thus, delay in hospital arrival maybe an important driver of disparities in tPA use and post-stroke outcomes among minorities (Cruz-Flores 2011).

Given the burden of stroke and poor outcomes among minority populations, there is a critical need for effective interventions that target minorities and emphasize early arrival to the hospital after stroke onset. Key steps to reducing delays in hospital arrival are 1) early recognition of stroke symptoms and 2) immediate activation of EMS (i.e. calling 911). Calling 911 immediately not only saves time in transit but also confers other important benefits such as advanced notification of stroke centers to prepare its emergency department to treat a stroke patient promptly and emergency pre-hospital care to manage neurologic deterioration or other medical complications.

**2. Hypothesis/Key Questions**

The overarching goal of the Community Engagement in Early Recognition and Immediate Action in Stroke (CEERIAS) study is to utilize a patient- and community-partnered approach to develop an effective intervention aimed at increasing early hospital arrival after stroke in 2 high-risk neighborhoods in Chicago. We hypothesize that through community partnerships will we be able to bridge the gap between knowledge (i.e., recognize symptoms of stroke) and action (i.e., call 911 early after stroke).

**3. Research Objectives and Purpose**

Specific Aim 1 (Development): Using qualitative methods (focus groups and content analysis), we will examine and identify personal, community, and cultural barriers to EMS for stroke among 3 race-ethnic groups (AA, Hispanic, and non-Hispanic whites); test and adapt our proposed interventional model for implementation in these groups and communities; and re-test and refine the intervention for implementation in 2 large multi-ethnic, disadvantaged neighborhoods in surrounds target PSCs (Holy Cross and Advocate Trinity Hospitals).

**Specific Aim 2 (Implementation):** To implement a culturally-adapted stroke awareness and action program, which will be delivered by community health workers (i.e. Stroke Promoters) and monitor its penetration and adoption using the RE-AIM framework in 2 large neighborhoods in Chicago (Holy Cross and Trinity Hospital catchment areas).

**Specific Aim 3 (Comparative Effectiveness):** To assess change in early hospital arrival and EMS use at 2 intervention hospitals (Holy Cross and Trinity) using an interrupted time-series analysis.

#### 4. Research Methods

##### **Specific Aim 1 (Development)**

**Description of Focus Group/Telephone Interview Participants:** Focus groups will gather a broad range of perspectives, beliefs, and experiences from persons from geographically diverse neighborhoods surrounding the 2 target PSCs. Because both laypersons and stakeholders present equally valid yet different points of view, we will conduct focus groups and telephone interviews for these two groups separately. Given our interest in understanding race-ethnic and neighborhood barriers, we will conduct 1 AA, 1 Hispanic, and 1 non-Hispanic white focus group per target neighborhood (total 6 layperson focus groups). These will be conducted in English and Spanish and participants will receive a \$50 honorarium. We will also conduct key informant telephone interviews of stakeholder/community leaders. We expect to successfully recruit 6-10 adults (age > 18 years) per layperson or stakeholders using a purposive strategy, recruiting subjects from each ethnic group in targeted neighborhoods. Since key informants will be generated from contacts with community organizations and advisory board members' input, we plan to recruit key informants using direct communications to individuals referred or recommended by our research team, CAB, and collaborating organizational partners.

**Conduct of Focus Group Interviews:** The purpose of the focus group is to explore and probe barriers to calling 911 for stroke. These considerations will form the basis for developing the community intervention best suited for each race-ethnic group that will produce change in EMS use and early hospital arrival after stroke. The focus group interviews will be as consistent as possible across all groups, utilizing the same focus group moderators for each race-ethnic group between the 2 neighborhoods. Based on our preliminary data and a review of the extant literature, the study team including our Community Advisory Board members (CAB), will develop a focus group guide to explore the barriers and facilitators to 911 calls in multi-ethnic communities. This guide will include a set of probing open-ended questions to encourage focus group participants to share personal experiences. Participating community partners (such as PSCs) with history of work in the Hispanic communities and the Spanish speaking CEERIAS Study Coordinator will assist with the translation of the Spanish language focus group guide, using a combination of the back translation method and group consensus (Brislin 1970), to conduct Spanish language focus groups. The Spanish language focus group guide will be reviewed by the investigative team and Hispanic community partners to ensure appropriate literacy level and cultural equivalence. Recruitment of focus group participants will be initiated by stakeholders selected from each neighborhood. The focus groups will last approximately 1.5 hours. All participants will sign an informed consent prior to participation. The sessions will be audio recorded and transcribed into Microsoft Word documents; transcripts in Spanish will be cross-checked for accuracy. Key informant interviews will be performed one-on-one by telephone using the focus group interview guide as reference. These interviews will take 30 minutes to complete, will be performed only in English, and will be audio recorded. Verbal consent will be obtained by telephone at the start of the interview. Only those who agree to participate and provide their verbal consent will continue with the interview.

**Analysis of the Focus Group Transcripts:** Transcripts will be imported into NVIVO qualitative analysis software for analysis. Data will be initially coded by the lead qualitative researcher on the team using a preliminary coding scheme based on the issues of interest. Once the data are coded using preliminary codes, transcripts will be sent to the remainder of the analysis team. Team members will read and suggest additional codes and/or make amendments to the themes identified in the preliminary coding. The coded data will allow for grouping of the comments into categories using the NVIVO software features that will be incorporated into the proposed intervention (MIP-PACT to ACT FAST program) and address barriers appropriately (i.e. comments about trust, costs, family/cultural dynamics) for application into minority populations. We will also compare the discussion across race-ethnic groups and neighborhoods. We anticipate that ideas arising from the focus groups may include suggestions for changes in content, context, and delivery of the community intervention. Using an adapted Delphi approach, we will confirm our findings with a representative from each focus group in an iterative process. For these a telephone interview approach, similar that described above for key informant interviews, will be used. Only those subjects who consented to being contacted for further follow-up interviews will be recruited for this phase. Up to 6 individuals, representing each focus group, will be recruited for telephone interviews.

Once the research team, based on the Delphi method, has reached consensus, the findings will be discussed with and reviewed by recruited community stakeholder focus group members as well as the CAB. Based on messages, content, teaching styles, and learning techniques suggested in the focus groups, along with input from our stakeholders and CAB, we will develop the final adapted strategy for broad dissemination within each of the racial/ethnic communities in the 2 neighborhoods (potentially 6 total adaptations). We anticipate that based on the focus group recommendations, there will be edits to the original PACT to ACT FAST materials that will be disseminated to the community, reflecting a more culturally sensitive and specific message. Once the interventions are adapted, we will pilot the interventions with a small sample of additional stakeholders and lay community members, likely 12 individuals total, and conduct cognitive interviews with this sample to evaluate the intervention. The cognitive interview will be conducted by telephone and last approximately 30 minutes. Answers will be recorded in a Word document and password protected. Subjects will be compensated \$25 for their time. Additional modifications of the intervention and messaging may be needed, based on these cognitive interviews, prior to implementation.

### **Specific Aim 2 (Implementation)**

*The protocol, evaluation forms, and consents for Aim 2 will be modified and informed by the results of Aim 1. An amendment outlining changes to the overall Aim 2 protocol will be submitted when appropriate. We present the general protocol below.*

**Stroke Promoters:** Year two of this project will involve the implementation of the focus group derived intervention. We will identify community stroke promoters and provide them with training on strategies to improve early recognition and EMS utilization for stroke, specifically culturally-adapted solutions to current barriers and cues to aid in stroke recognition and immediate action. We anticipate that stroke promoter will come from five core community groups: hospital/clinics, public officials, public schools, faith-based organizations; and firehouses. Our implementation and recruitment of stroke promoters will be based on successful completion of focus groups.

**Stroke Promoter Training:** Stroke Promoters in the adapted MIP-PACT program will engage in interactive discussions with community leaders and health care professionals on strategies to enhance patient and bystander self-efficacy and increase public knowledge about stroke warning signs, treatments, and expected outcomes.

Each adapted MIP-PACT training program will include up to 15 stroke promoters (representatives from community organizations) and will be a maximum of four hours in length. Immediately preceding the training program, all attendees will receive a phone call confirming their attendance, also outlining the scope of the project and agenda for the tour (Appendix 3). Stroke promoters will be recruited concurrently at the 2 primary stroke centers in a total of 12 waves (20 Stroke Promoters trained each month or 240 total) throughout the first 6 months of year 2.

At the conclusion of the program, the participants will complete a Training Evaluation Form, sign the PACT to ACT FAST, and obtain educational materials for community dissemination that will include culturally sensitive and adapted FAST materials with information on how to restock supplies from the CEERIAS Community Navigator on a monthly basis. Each Promoter will be tasked with disseminating the educational materials to their constituents. They will be asked to present the program at least twice monthly for 6 months.

After each Promoter-led educational community event, the Stroke Promoters will also complete electronic Activity Evaluation Forms documenting the name of the event, location, numbers of persons attending, and rate the enthusiasm of the participants. Community participants who attended educational events will be asked to complete Participant Activity Evaluation Forms on paper (5 minutes), sign the PACT to ACT FAST certificate (1 minute), and the Participant Interest Form (5 minutes). These forms ask the participant to provide feedback about the presentation, the presenter, and their interest in being a Stroke Promoter and completing a telephone survey. All paper forms will be de-identified and collected by the Community Navigator and returned to Northwestern University for electronic data entry and storage.

Each Promoter will receive \$732 in two installments for the training and ongoing participation in their outreach efforts. We plan to compensate those who attend the training and are engaged with the outreach efforts as outlined during the training class. If there is no level of engagement post training, they will not receive the full compensation. They will need to submit to the study coordinator a W-2 or W-9 and sign a contracted services form. Payments will be mailed based on the level of engagement after the training.

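### Do the Stroke Promoter training figures fail to add up to the stated 240?

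*Combined protocol and SAP*

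**What the plan says.** The figures stand together in section 4 of the Combined protocol and SAP, under Specific Aim 2 (Implementation), Stroke Promoter Training.

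- Size of a training program: "Each adapted MIP-PACT training program will include up to 15 stroke promoters".
- Place of recruitment: "Stroke promoters will be recruited concurrently at the 2 primary stroke centers".
- Schedule and total, in the same sentence: "in a total of 12 waves (20 Stroke Promoters trained each month or 240 total) throughout the first 6 months of year 2".
- Task of each promoter after training: "They will be asked to present the program at least twice monthly for 6 months".

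The Aim 2 section opens with a note that its content is a general outline, to be revised by amendment once the Aim 1 results are known.

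**The concern.** Taken without the reference to two centers, the parenthesis "20 Stroke Promoters trained each month or 240 total" seems to contradict the period "throughout the first 6 months of year 2": six months at 20 a month yields half the stated total. The 15-person cap seems to add a second contradiction, since 12 full programs would train 180.

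If the target really could be 120, 180 or 240, the planned size of the intervention would be unclear by up to a factor of two. Training 120 promoters would then be full delivery on one reading and half delivery on another. Section 3 commits the study to monitoring penetration and adoption under RE-AIM, and Aim 3 estimates the effect of what was delivered, so the question is a fair one to ask.

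**Working it through.** Inputs, all from the Stroke Promoter Training paragraphs: 2 centers recruiting concurrently; 12 waves in total; 6 months; 20 promoters a month; 240 promoters in total; at most 15 per training program; at least 2 presentations a month for 6 months, so at least 2 x 6 = 12 per promoter.

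**Step 1. Reproduce the plan's figure.** One wave per center per month gives 2 x 6 = 12 waves, the stated number. With 20 promoters per wave, 12 x 20 = 240, the stated total. Centers, months, waves, rate and total all agree when the 20 is the monthly intake at each center.

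**Step 2. Try the other readings.**

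| Reading | Sum | Promoters | Minimum presentations (x 12) |
|---|---|---|---|
| 20 a month at each center, 6 months | 2 x 6 x 20 | 240 | 2,880 |
| 20 a month over both centers, 6 months | 6 x 20 | 120 | 1,440 |
| 12 waves, each a single full program | 12 x 15 | 180 | 2,160 |
| 20 a month over both centers, 12 months | 12 x 20 | 240 | 2,880 |

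The second and third readings miss the stated total. The fourth reaches it, but only by doubling the stated training period. Only the first satisfies the number of waves, the period and the total together.

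**Step 3. Check the cap.** The cap applies to a training program, whereas the 12 are waves of recruitment. The text does not say that a wave is one program. A wave of 20 needs two programs, for example two of 10, which makes 12 x 2 = 24 programs. If waves were pooled, 240 / 15 = 16 full programs would be the minimum. The plan states no number of programs, so neither figure contradicts it. The 180 arises only if wave and program are taken to be the same thing.

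**Step 4. See where the count is used.** The power statement in the Statistical Analysis section rests on 60 monthly points, 40 before and 20 after the intervention, a step from 50% to 55%, an SD of 3% and an autocorrelation of 0.3. The segmented regression described under Aim 3 works on monthly hospital proportions. The number of promoters appears in neither. RE-AIM is named in section 3 without any denominator tied to 240.

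**The case for a change.** The strongest reply is that the words for a per-center rate are not on the page. The phrase "20 Stroke Promoters trained each month or 240 total" follows directly after "in a total of 12 waves", so a reader may well take the 20 as an overall figure. Twelve monthly waves of 20 would also give 240, over a training period twice as long. Since the power statement assumes a flat step over 20 post-intervention months, a 12-month rather than a 6-month build-up would leave less of that period at full delivery. And even the per-center reading needs waves to be split, which is not stated. Fixing the target in advance would also stop a denominator being chosen after delivery is known.

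Part of this stands. The missing words are a real omission, and so is the number of programs per wave. The rest carries less weight. The 12-month reading contradicts an explicit statement of the period and makes no use of the two concurrent centers. No total other than 240 is printed anywhere, so there are not three competing targets. Actual delivery will also be visible: trainees complete an evaluation form at the end of training, and promoters file a form after every event. The number trained and the events held can therefore be reported as observed, whatever the planning figure was.

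**Conclusion.** The concern does not hold as an arithmetic error. The stated 240 equals 2 centers x 6 months x 20 exactly, and the 12 waves follow from the same product. The apparent shortfalls to 120 and 180 come from leaving out the second center and from treating a wave as a single training program.

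What is left is a gap in wording: the monthly 20 is not labelled as per center, and the division of a wave of 20 into programs of up to 15 is not described. Staff running the training would settle both in practice, and the announced Aim 2 amendment is a natural place to record them. The conclusion assumes that the per-center reading is the intended one, which the document does not say outright but which is the only one tried that fits the stated waves, period and total. Even if that assumption were wrong, the power calculation and the specified time-series model would be unaffected, because neither uses the promoter count. No change to the plan is needed.

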### **Specific Aim 3 (Comparative Effectiveness-Behavior and Action)**

To compare the effectiveness of these interventions on behavior or action, we will monitor early hospital arrival and EMS use for stroke over a 60-month period at the 2 intervention hospitals using an interrupted time-series analysis. Early hospital arrival will be defined as the proportion of stroke patients arriving within 3 hours from symptom onset while EMS utilization (%) will be defined as the proportion of stroke patients arriving to the emergency department by EMS. Segmented regression analysis will be conducted to estimate whether and how much the intervention changes EMS utilization in each of the 2 target hospitals and in aggregate at both hospitals. Autoregressive error will account for correlations of the data across time points. In secondary analyses, temporal trends in early hospital arrival and EMS utilization from 2 pre-selected non-intervention Chicago hospitals (St. Elizabeth and Swedish Covenant) and from hospitals in St. Louis, a comparable Midwestern city, will be compared with the 2 intervention neighborhoods/hospitals in Chicago.

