## 6. Statistical Analysis

**Statistical Considerations and Power:** Existing data of monthly onset-to-hospital arrival times and EMS utilization from January 2013 to December 2017 (five years; n=60 months) will be obtained through AHA. We will assume approximately one-third (20 months) will be post-intervention periods. The effect size will be defined as the sum of expected slope change (i.e. monthly change) over the standard deviation. Table 1 shows the study power by autocorrelation level and effect size. Assuming pre-intervention EMS use rate is 50% on average (SD: 3%; 40 months of data) and post-intervention EMS use rate is 55% on average (SD: 3%; 20 months of data; auto-correlation=0.3) and no trend change (“flat”) in pre- or post-intervention periods, this 5% step-increase will be significant at 90% power at a significance level of 0.05. For a 10% step-increase (the goal) with the same assumptions, power is nearly 100%.

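### Aim 3 looks for a change in EMS use in three overlapping series with no deciding series, parameter or outcome order; letting any one count roughly doubles the false-positive rate

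*Combined protocol and SAP*

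**What the plan says.** **Outcomes.** Section 2 sets out to "develop an effective intervention aimed at increasing early hospital arrival after stroke in 2 high-risk neighborhoods in Chicago", and its hypothesis is to "bridge the gap between knowledge (i.e., recognize symptoms of stroke) and action (i.e., call 911 early after stroke". Section 3 gives Aim 3 as "To assess change in early hospital arrival and EMS use at 2 intervention hospitals (Holy Cross and Trinity) using an interrupted time-series analysis". The first sentence of Specific Aim 3 (Behavior and Action) in section 4 puts both outcomes under the interrupted time series, and both are then defined. Neither is called primary.

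**Series.** The segmented-regression sentence concerns EMS use only. Its purpose is "to estimate whether and how much the intervention changes EMS utilization in each of the 2 target hospitals and in aggregate at both hospitals". The next analyses are the ones marked as lower in rank: "In secondary analyses, temporal trends in early hospital arrival and EMS utilization from 2 pre-selected non-intervention Chicago hospitals", together with hospitals in St. Louis.

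**Parameter.** Section 6, Statistical Analysis, states: "The effect size will be defined as the sum of expected slope change (i.e. monthly change) over the standard deviation". Its worked example takes EMS use from 50% to 55% with no trend before or after, and says "this 5% step-increase will be significant at 90% power at a significance level of 0.05". It continues: "For a 10% step-increase (the goal) with the same assumptions, power is nearly 100" (per cent). The Aim 3 limitations in section 7 again quote power for EMS use only.

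The opening pages and Table 1 of the power section are not in the text supplied. Nothing in the remaining text ranks the outcomes or series, says whether level, slope or both is tested, or adjusts for multiple tests.

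**The concern.** The plan does not say how to read a mixed result: one hospital significant but not the aggregate, a level change without a slope change, or EMS use up without earlier arrival. If that is decided once the data are in, each pattern can be offered as evidence that the program worked.

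The parameter matters in practice because exposure builds up. Under Specific Aim 2, promoters are trained in waves over six months and then asked to present for six months. A gradual rise is therefore at least as plausible as the flat step in the worked example, and the two shapes are picked up by different terms of a segmented model.

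**Working it through.** **Inputs from the plan (section 6, Statistical Analysis).** 60 months split 40/20, SD 3 points, autocorrelation 0.3, alpha 0.05, steps of 5 and 10 points. Admissions (section 5 table): 413 at Trinity and 353 at Holy Cross, total 766.

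**Assumptions.** Two-sided tests, AR(1) errors (the order is not stated), and between-hospital correlation r of 0 to 0.3 (not given).

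**1. The plan's own power figure.** With Σ_ij = 9 × 0.3^|i−j|, the generalised least squares variance is (X′Σ⁻¹X)⁻¹. Power is from the noncentral t with noncentrality 5/SE.

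| Model | SE of step | 5/SE | df | Power, 5-point step |
|---|---|---|---|---|
| Level only | 1.09 | 4.61 | 58 | 99.5% |
| Level + common trend | 1.81 | 2.76 | 57 | 77.4% |
| Level + trend + slope change | 2.01 | 2.48 | 56 | 68.5% |

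Hand check of the first row: 3 × √(1/40 + 1/20) × √(1.3/0.7) = 1.12, close to 1.09. One-sided, the three powers are 99.8%, 86.0% and 79.1%. None is the stated 90%. The 10-point step gives 99.8% or more in all three models, so the near-certain power for the goal reproduces. A joint 2-df F test of level and slope has 66.9% power for the 5-point step (noncentrality 7.61, critical value 3.16 on 2 and 56 df).

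**2. False positives over the three EMS series.** Let Z_T and Z_H be the null statistics for Trinity and Holy Cross. Weighting by admissions, at r = 0 the aggregate statistic is √(413/766) Z_T + √(353/766) Z_H = 0.734 Z_T + 0.679 Z_H. Simulation with several million draws, critical value 1.96:

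| | r = 0 | r = 0.3 |
|---|---|---|
| At least one of three significant | 11.5% | 10.5% |
| A hospital significant, aggregate not | 6.5% | 5.5% |
| At least one significant in the beneficial direction | 5.8% | 5.3% |

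Check: the aggregate alone gives 5.0%, and 5.0 + 6.5 = 11.5; 5.0 + 5.5 = 10.5. Ratios to a single test are 11.5/5 = 2.3 and 10.5/5 = 2.1 two-sided, and 5.8/2.5 = 2.3 and 5.3/2.5 = 2.1 in the beneficial direction.

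**3. Level and slope both tested in one series.** In the full model the two estimates have correlation −0.43. The chance that at least one is falsely significant is 9.2%.

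**4. Shape of effect against parameter.** Take a linear rise from 0 in the first post-intervention month to 5 points in month 60, that is 5/19 = 0.263 points a month.

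| Test | Power for the ramp |
|---|---|
| Level, level-only model (coefficient 2.44, SE 1.09) | 60% |
| Level, common-trend model (coefficient 1.44, SE 1.81) | 12% |
| Level, full model | 5% |
| Slope change, full model (0.263/0.160 = 1.65) | 37% |
| Joint test, full model | 34% |

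For a pure step, the slope test in the full model also stays at 5%.

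**5. How far the SD of 3 can be relied on.** 766/12 is about 64 admissions a month. Pooled EMS use in the section 5 table is (413 × 0.44 + 353 × 0.36)/766 = 40.3%. Binomial sampling alone gives a monthly SD of 100 × √(0.403 × 0.597/63.8) = 6.1 points, or 6.3 at 50%. With that SD the powers in step 1 become 58-60%, about 26% and about 22%.

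**The case against.** **The plan says estimate, and does not say that one significant series is enough.** True, and hospital results may be meant descriptively. But the sentence asks whether EMS use changes as well as by how much, it asks this of all three series, and only the external comparisons are labelled secondary. The doubling follows if any series may count, and the plan does not exclude that.

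**The false-positive rate overstates false success.** A reader might take 10.5-11.5% as the chance of wrongly declaring benefit. It counts both directions; the beneficial figure is 5.3-5.8%. The ratio to a single test is the same.

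**A reader might infer that a level test always misses a gradual rise.** That holds only in the full model. A level-only model finds the ramp above with 60% power, and the plan does not say which model it means.

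**A reader might infer that early arrival was left out of the analysis, or multiply the error rate up over both outcomes and both parameters in every series.** Neither is supported. Early arrival is in the first sentence of the Aim 3 method, and the plan does not state those further tests. What is missing is early arrival from the model sentence and from the power text supplied.

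**EMS use is the implied main outcome.** The model sentence and the power text point that way, and section 6 attaches the goal to an EMS step. Section 2 points to early arrival, so the implication does not settle the order.

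**The effect-size wording and Table 1.** The definition speaks of a sum of slope change, which could mean an accumulated change, and Table 1 might clarify it or cover early arrival. This softens the contradiction with the step example. It does not supply a named test.

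**Hospital-level inference may be wanted.** Aim 1 foresees adaptations by neighborhood. That is a fair reason to allow a gated hospital test, as in the fix.

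**Conclusion.** The point holds for the text supplied, and the sponsor should act on it. Three EMS series with no deciding one give about twice the nominal false-positive rate: 10.5-11.5% two-sided, or 5.3-5.8% against 2.5% for benefit. In 5.5-6.5% of null cases a hospital would be significant while the aggregate is not. These figures assume one parameter per series, two-sided 0.05, and r between 0.3 and 0. If level and slope are both tested in one series, which the plan leaves open, the rate is 9.2%.

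The choice of model and parameter is substantive, since it moves power for the plan's own 5-point step between 68.5% and 99.5% at SD 3. It might be inferred that the stated 90% is simply wrong. The documents support less: none of the three models above gives 90%, and the model behind it is not stated. The likely understatement of the SD is a separate matter. It means only that these power figures should not be taken as reassurance that splitting alpha would cost little.

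**What to change.** Amend Specific Aim 3 (Behavior and Action) in section 4 and the power text in section 6, before post-intervention data are examined.

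1. **Series.** Make the aggregate two-hospital series primary and report each hospital as an estimate with a confidence interval. If hospital-level claims are wanted, test the hospitals only after the aggregate is significant, and say where those tests stand relative to the second outcome.
2. **Parameter.** Name one deciding test: level change, slope change, or a single joint test of both. State the terms in the model, and align the effect-size definition and worked example with it. The joint test avoids betting on the shape of the effect, at 66.9% power for the 5-point step under SD 3.
3. **Outcomes.** State that the segmented regression applies to early arrival as well, and put the two outcomes in a fixed order, each at 0.05. The sponsor chooses the order: section 2 points to early arrival, the model and power text to EMS use.

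The cost is wording in two places and no new data collection. The price in claims is that a single hospital cannot carry a confirmatory claim on its own, and the second outcome cannot be claimed if the first fails.
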